8.2 Rationale for study design

This study evaluates for the first time the dose-response related vasodilative effects of C21.

Suggested dose escalation design and i.a. infusion has been widely used in the FBF design for the past 80 years contributing to exploring human vascular physiology in vivo [11] and is considered as a golden standard in the assessment of vascular function.

Strain-gauge venous occlusion plethysmography will be use as a method for assessment of the primary endpoint (see Section 6.4).

The study design involves careful monitoring of the subject's well-being. Furthermore, by infusing IMP locally, drug-induced changes in blood pressure and cardiovascular reflexes can be minimised.

8.2.1 Selection of starting dose and rationale for planned dose escalation

The pre-defined doses of C21 (3, 10, 30, 100 and 200 μ g/min) have been selected to achieve sufficient coverage of the receptor during the plethysmography measurements. The required dose of C21 to produce a local effect in the forearm is estimated based on prior similar studies [4]. The maximum dose of 200 μ g/min has been chosen to ensure that a full dose-response curve is achieved. The total dose at the 200 μ g/min dose level will not exceed 1 mg (see Section 10.5, Table 10.5-1). Overall, C21 was well tolerated at doses up to 100 mg twice daily administered for up to 8 days [8].

Sodium nitroprusside is selected as a positive control due to its potent vasodilative properties. The doses of Nipruss[®] (sodium nitroprusside) (0.8, 1.6, and 3.2 μ g/min) have been selected to achieve vasodilative effects demonstrated in previous experimental studies [9, 10]. The total dose at the highest dose level will not exceed 16.0 μ g (see Section 10.5, Table 10.5-2).

9 STUDY POPULATION

Prospective approval of protocol deviations from eligibility criteria, also known as protocol waivers or exemptions, will not be permitted.

9.1 Recruitment

The subjects will be recruited from CTC's database of healthy volunteers and/or through advertisement in social media.

9.2 Screening and enrolment log

Investigators must keep a record of all subjects screened even if they were not subsequently included in the study. This information is necessary to verify that subjects were selected without bias. The reason for screen failure should be stated for all subjects screened but not included. The reason for withdrawal should be stated for all subjects included but not completed.

A screening number will be allocated to each subject in connection to the informed consent process at the screening visit (Visit 1). The screening number is generated automatically in the electronic case report form (eCRF). The screening number will allow identification of subjects irrespective of their possible eligibility for the study.

Subjects included will be assigned a subject number (e.g. 101, 102 etc).

If a subject cannot receive the planned doses of IMP within 30 days after screening (*i.e.* the time interval between signing informed consent until IMP administration), the subject should be re-screened before being included in the study.

9.3 Number of subjects

Approximately 10 subjects will be screened to achieve 5 included and evaluable subjects. For replacements of subjects who discontinue from the study, see Section 9.8.4.

9.4 Inclusion criteria

For inclusion in the study, subjects must fulfil the following criteria:

- 1. Willing and able to give written informed consent for participation in the study and to comply with study requirements.
- 2. Healthy male subject aged 18-45 years inclusive at the time of signing the informed consent.
- 3. Body mass index (BMI) \geq 18.5 and \leq 30.0 kg/m².
- 4. Male subjects must be willing to use condom or be vasectomised or practice sexual abstinence to prevent pregnancy and drug exposure of a partner and refrain from donating sperm from the date of dosing until 4 weeks after dosing with the IMP. Their female partner of child-bearing potential must use contraceptive methods with a failure rate of < 1% to prevent pregnancy (combined [oestrogen and progestogen containing] hormonal contraception associated with inhibition of ovulation [oral, intravaginal, transdermal], progestogen-only hormonal contraception associated with inhibition of ovulation [oral, intravaginal, contraception]

injectable, implantable], intrauterine device [IUD]or intrauterine hormone-releasing system [IUS]) from at least 4 weeks prior to dose to 4 weeks after last dose).

5. Clinically normal medical history, physical findings, vital signs, ECG and laboratory values at the time of screening, as judged by the Investigator.

9.5 Exclusion criteria

Subjects must not enter the study if any of the following exclusion criteria are fulfilled:

- 1. History of any clinically significant disease or disorder which, in the opinion of the Investigator, may either put the subject at risk because of participation in the study, or influence the results or the subject's ability to participate in the study.
- 2. History of thrombotic disease, vascular disorder, or severe bleeding disease.
- 3. Poor brachial artery access.
- 4. Any clinically significant illness, medical/surgical procedure, or trauma within 4 weeks of Day 1 (Visit 2).
- 5. Malignancy within the past 5 years with the exception of basal cell or squamous epithelial carcinomas of the skin that have been resected with no evidence of metastatic disease for 3 years.
- 6. Any planned major surgery within the duration of the study.
- 7. Any positive result on screening for serum hepatitis B surface antigen, hepatitis C antibody and human immunodeficiency virus (HIV).
- 8. After 10 min supine rest at the time of screening, any vital signs values outside the following ranges:
 - Systolic blood pressure <100 or >140 mmHg, or
 - Diastolic blood pressure <50 or >90 mmHg, or
 - Pulse <45 or >90 beats per minute (bpm)
- 9. Prolonged QTcF (>450 ms), cardiac arrhythmias or any clinically significant abnormalities in the resting ECG at the time of screening, as judged by the Investigator.
- 10. History of severe allergy/hypersensitivity or ongoing allergy/hypersensitivity, as judged by the Investigator, or history of hypersensitivity to drugs with a similar chemical structure or class to the IMPs, including any of the excipients of the IMPs.
- 11. Regular use of any prescribed or non-prescribed medication including antacids, analgesics, herbal remedies, vitamins, and minerals within 2 weeks prior to Day 1 (Visit 2), at the discretion of the Investigator.
- 12. Regular use of non-steroidal anti-inflammatory drugs (NSAIDs) or acetylsalicylic acid (ASA) within 2 weeks prior to Day 1 (Visit 2).
- 13. Vaccination within 1 week prior to dosing or plans to receive any vaccine during the study conduct.
- 14. Planned treatment or treatment with another investigational drug within 3 months prior to Day 1 (Visit 2). Subjects consented and screened but not dosed in previous phase 1 studies are not excluded.

- 15. Current regular smokers or users of nicotine products. Irregular use of nicotine (*e.g.* smoking, snuffing, chewing tobacco) less than 3 times per week is allowed before the screening visit.
- 16. History of alcohol abuse or excessive intake of alcohol, as judged by the Investigator.
- 17. Presence or history of drug abuse, as judged by the Investigator.
- 18. Positive screen for drugs of abuse or alcohol at screening or Day 1 (Visit 2), prior to administration of the IMP.
- 19. History of, or current use of, anabolic steroids.
- 20. Inability to refrain from consuming caffeine-containing beverages during Day 1 (Visit 2), *e.g.* propensity to develop headaches when refraining from caffeine-containing beverages.
- 21. Plasma donation within 1 month of screening or blood donation (or corresponding blood loss) during the 3 months prior to screening.
- 22. Investigator considers the subject unlikely to comply with study procedures, restrictions and requirements.

9.6 Restrictions during the study

The subjects must be willing to comply with the following restrictions during the entire study duration *i.e.* from screening to the end-of-study contact.

9.6.1 General restrictions

- Contraception Requirements: The male subjects are expected to use condom to prevent pregnancy and drug exposure of a partner and refrain from donating sperm from the date of dosing until 4 weeks after last dose of the IMP. Fertile female partners are expected to use contraceptive methods with a failure rate of < 1% to prevent pregnancy (for details, refer to inclusion criterion no. 4).

- Meals: A standardised breakfast or lunch, depending on the time of the day, will be served to all subjects 60 min prior to the first FBF measurement.
- Alcohol: Consumption of alcohol is not allowed within 48 hours prior to screening (Visit 1) and Day 1 (Visit 2).
- Drugs of abuse: Use of drugs of abuse is not allowed during the study (from the screening visit to the end-of-study contact).
- Coffee: No coffee or caffeine-containing drinks are allowed on Day 1 (Visit 2), until leaving the clinic. Subjects may be served caffeine free coffee.
- Xanthine or taurine containing products/beverages: Energy drinks (*e.g.* Red Bull) are not allowed on Day 1 (Visit 2), until leaving the clinic.
- Nicotine: Smoking or use of nicotine-containing products is not allowed from screening until end of Day 1 (Visit 2).
- Grapefruit and grapefruit containing products: Consumption of grapefruit and/or grapefruit containing products or Seville oranges is not allowed during the study.
- Exercise: The subjects must refrain from strenuous exercise (defined as greater than 70% of the maximal pulse rate for 1 hour or more) for 24 hours before Day 1 (Visit 2).

- Blood donation: The subjects must not donate blood or plasma during the study until 3 months after the last dose of IMP.
- Participation in other clinical studies: Study subjects are not allowed to participate in any other interventional clinical study during the study period.

9.6.2 Prior and concomitant therapy

Prohibited medication

Regular use of any prescribed or non-prescribed medication including antacids, analgesics, herbal remedies, vitamin supplements and minerals from 2 weeks prior to the first administration of IMP (Day 1) until the end-of-study contact, at the discretion of the Investigator.

Any use of prescribed or non-prescribed medication including NSAIDS/ASA, antacids, analgesics, herbal remedies, vitamin supplements and minerals from the first administration of IMP (Day 1) until the end-of study contact is not allowed, except as detailed below.

Allowed medication

- Paracetamol in doses up to 2,000 mg/day for a maximum of 3 consecutive days. If this amount of paracetamol is not sufficient for treatment of the subjects, withdrawal should be considered.
- Nasal decongestants without cortisone, antihistamine, or anticholinergics for a maximum of 10 days.

Other medications considered necessary for the subject's safety and wellbeing may be given at the discretion of the Investigator during the study period. Following consultation with the Sponsor, the Investigator will determine whether the subject should continue in the study.

9.7 Screen failures

Screen failures are defined as subjects who consent to participate in the clinical study but do not fulfil all eligibility criteria and are not subsequently included in the study. A minimal set of screen failure information is required to ensure transparent reporting of screen failure subjects. Minimal information includes documentation of signed and dated informed consent form (ICF) and reason(s) for screening failure.

Re-screening can be performed once/subject if any of the following were reasons for screening failure or non-inclusion (as judged by the Investigator):

- Practical reasons
- Non-significant medical conditions (*e.g.* influenza, nasopharyngitis)
- Plasma or blood donation outside allowed time windows

For subjects who are re-screened, a new screening number will be assigned and a new, signed ICF will be collected.

9.8 Subject withdrawal

9.8.1 General withdrawal criteria

Subjects are free to discontinue their participation in the study at any time and for whatever reason without affecting their right to an appropriate follow-up investigation or their future care. If possible, the reason for withdrawal of consent should be documented.

Subjects may be discontinued from the study at any time at the discretion of the Investigator. Reasons for discontinuation include:

- Subject decision
- Severe non-compliance to clinical study protocol (CSP) procedures, as judged by the Investigator and/or Sponsor
- Subject is lost to follow-up
- Significant AEs posing a risk for the subject, as judged by the Investigator and/or Sponsor
- Withdrawal of informed consent to the use of biological samples

9.8.2 Withdrawal in case of extravascular cannulation

In case of accidental extravascular infusion of C21 or Nipruss[®] the subject will be withdrawn from further infusions.

9.8.3 Procedures for discontinuation of a subject from the study

A subject who prematurely discontinues participation in the study will always be asked about the reason(s) for discontinuation and the presence of any AEs. If a subject withdraws consent, the Investigator must ask the subject if he is willing, as soon as possible, to be assessed according to the procedures scheduled for the end-of-study contact. Any ongoing AEs will be followed as described in Section 11.3.1.15.

The primary reason for discontinuation/early withdrawal must be specified in the eCRF and final drug accountability must be performed.

9.8.4 Subject replacement

Subjects who discontinue prior to IMP administration may be replaced. Subjects who discontinue after initiation of IMP administration, for other reason than occurrence of an AE assessed as related to the IMP, may be replaced.

9.9 Randomisation and blinding

Randomisation will not be used. This is an open-label study and all subjects will receive the same IMP and undergo the same study procedures.

10 TREATMENTS

10.1 Identity of investigational medicinal products

10.1.1 Test product

C21 is a novel first in class selective AT_2R agonist. Activation of AT_2R causes dilatation of blood vessels and inhibition of inflammation, apoptosis, and fibrosis, and is thus considered to play a beneficial counter-regulatory role to the effects of AT_1R activation.

C21 solution for local i.a. infusion will be provided in concentrations of 30 μ g/mL and 100 μ g/mL. These concentrations will be diluted with 0.9% saline to achieve the two lower doses (see Section 10.5).

More detailed information about the IMP composition can be found in the Investigational Medical Product Dossier.

10.1.2 Comparator product

A positive control solution will be prepared from Nipruss[®] powder for solution (active ingredient sodium nitroprusside dihydrate) due to the potent vasodilative properties of sodium nitroprusside.

Nipruss[®] is provided as a pink hygroscopic powder in amber glass ampoules. Each ampoule contains 60 mg sodium nitroprusside dihydrate powder corresponding to 53 g water free sodium nitroprusside.

The powder will be dissolved in water for injection solutions or in a 5% glucose solution. This concentrated solution will be diluted with a 5% glucose solution to achieve the doses given in Section 10.5.

10.2 Manufacturing, packaging, and labelling and release

The C21 solution will be manufactured, packed, and labelled by Ardena, Mariakerke, Belgium. The primary packaging for the bulk solution is 10 mL vials: $20 \times 30 \mu g/mL$ and $30 \times 100 \mu g/mL$. The vials will be packaged in an outer cartoon (secondary package). The IMP will be released and shipped to site by ClinStorage AB, Solna, Sweden.

Nipruss[®] powder for solution, 60 mg/ampoule, will be ordered from and labelled for the clinical study by Apoteket AB, Clinical Trial Unit, Uppsala, Sweden.

Labels will comply with applicable Good Manufacturing Practice (GMP), with Annex 13 of the European Union Good Manufacturing Practice regulations and local regulatory requirements [15].

10.3 Conditions for storage

The C21 solution should be stored refrigerated at +5° C (+2 °C to +8 °C).

The Nipruss[®] powder should be stored at room temperature (+15 °C to +25 °C) protected from light. The prepared solution must be protected from light by using coloured or covered tubes and syringes. The prepared solution should be used immediately following preparation. Storage of the prepared solution for a maximum of 8 hours in +2 °C to +8 °C is allowed, if needed.

CONFIDENTIAL

Temperature logs will be kept for the area where the IMP is stored. The temperature should be noted daily (working days only unless automatic temperature readings are available).

10.4 Preparation and accountability

Preparation of IMPs will be done by qualified personnel, *i.e.* a site pharmacist or a registered nurse, in a dedicated room at CTC. Detailed instructions for the preparation and handling of the C21/Nipruss[®] solutions will be described in a separate *IMP Handling Instruction*.

CTC and the Investigator will maintain a *Storage and Accountability Log* as well as a *Drug Dispensing Log* detailing the dates and quantities of study medication received, prepared, and used for each subject and study medication returned or destroyed at the end of the study. Any discrepancies between prepared and returned IMP must be explained and documented. Products deliberately and/or accidentally destroyed by the site must be accounted for.

10.5 Treatment administration

The IMP solutions will be infused through a catheter placed in the brachial artery of the nondominant arm using standard hospital procedures for arterial cannulation.

Ascending doses of C21 (3, 10, 30, 100 and 200 μ g/min) will be administered to each subject with an infusion rate of 1 mL/min or 2 mL/min for the 200 μ g/min dose. Each infusion will last for 5 min. The C21 doses will be separated by a wash-out period of at least 15 min.

For the lower doses (3 μ g/mL and 10 μ g/min) the 30 μ g/mL and 100 μ g/mL solutions will be diluted 1:10 with 0.9% saline.

The doses of C21 are displayed in Table 10.5-1.

Dose (µg/min)	Infusion rate (mL/min)	Concentration (µg/mL)	Infusion time (min)	Total dose (μg)
3	1	3	5	15
10	1	10	5	50
30	1	30	5	150
100	1	100	5	500
200	2	100	5	1,000

Table 10.5-1 C21 doses

Following a 20 min resting period after the last C21 dose, i.a. infusions of sodium nitroprusside solution (Nipruss[®]) will be administered as a positive control. Ascending doses of 0.8, 1.6, and 3.2 μ g/min will be administered at an infusion rate of 1 mL/min. Each infusion will last for 5 min. The doses will be separated by a wash-out period of at least 15 min.

The doses of sodium nitroprusside are displayed in Table 10.5-2.

Dose (ug/min)	Infusion rate (mL/min)	Concentration (ug/mL)	Infusion time (min)	Total dose (ug)
0.8	1	0.8	5	4.0
1.6	1	1.6	5	8.0
3.2	1	3.2	5	16.0

Table 10.5-2 Sodium nitroprusside doses

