Infusions of sodium nitroprusside solution (Nipruss[®]) will be performed as a positive control, using the same methodology as described above. Ascending doses of 0.8, 1.6, and 3.2 μ g/min will be administered. A flow-chart of the Nipruss[®] dosing and FBF measurement schedule is presented in Figure 2.

Figure 2 Dosing and measurement flow-chart for Nipruss[®] infusions

Safety assessments (blood pressure, pulse, electrocardiogram [ECG], and safety laboratory parameters) will be performed prior to first dose of IMP and before the subject leaves the clinic. Any occurrence of AEs during the procedure will be recorded.

After removal of the arterial catheter a compression bandage will be applied to prevent bleeding. Written instructions regarding how to handle the bandage, how to manage symptoms and when and how to contact the Investigator if necessary, will be provided to the subject before leaving the clinic.

A follow-up phone call (end-of-study) will be performed 7 to 10 days after the treatment visit (Visit 2).

Investigational med Investigational medicinal product, dosage and mode of administration

Test product

C21 is a novel first in class selective AT_2R agonist. Activation of AT_2R causes dilatation of blood vessels and inhibition of inflammation, apoptosis, and fibrosis, and is thus considered to play a beneficial counter-regulatory role to the effects of angiotensin II type 1 receptor (AT_1R) activation.

C21 solution for local i.a. infusion will be provided in concentrations of 30 μ g/mL and 100 μ g/mL. These concentrations will be diluted with 0.9% saline to achieve the two lower doses. The solution will be infused through a catheter placed in the brachial artery. Ascending doses of 3, 10, 30, and 100 μ g/min will be administered to each subject with an infusion rate of 1 mL/min. For the dose of 200 μ g/min, the infusion rate will be 2 mL/min. Each infusion will last for 5 min.

Comparator product (positive control)

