6.4 Venous occlusion plethysmography

Venous occlusion plethysmography has been used extensively to study human vascular physiology *in vivo*, including i.a. drug administration. In fact, forearm venous occlusion plethysmography with local brachial artery infusion has become one of the golden standards in the assessment of vascular function in health and disease, and an accurate, reproducible and convenient method to assess the effect of new vasoactive drugs and hormones in humans *in vivo*. The advantage of the plethysmography technique is that drugs can be given at doses 10 to 100 times below those causing systemic effects because forearm blood flow (FBF) (<50 mL/min) is around 100-fold lower than cardiac output. Therefore, the effects on resistance vessels can be studied without invoking systemic effects or neurohormonal reflexes, minimising the potential for side-effects and toxicity [11].

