11.2 Efficacy assessments

11.2.1 Strain-gauge venous occlusion plethysmography

Measurements of FBF will be performed using a CE-marked automated strain-gauge venous occlusion plethysmography equipment providing on-line measurements; Bergenheim, Elektromedicin, Göteborg, Sweden.

The underlying principle of this method is that when the venous return from the forearm is briefly interrupted by inflating a cuff placed around the upper arm to well above venous pressure but below diastolic pressure, and arterial inflow continues unimpeded, the forearm swells at a rate proportional to the rate of arterial inflow. Changes in forearm volume result in a corresponding change in arm circumference and thus strain-gauge length, which can be detected as an alteration in electrical resistance of the gauge, and thus potential difference [16].

The subject will be placed resting in a comfortable supine position in a quiet room with normal room temperature (+20 °C to +25 °C) [14]. Both forearms must be positioned above the level of the heart to ensure adequate venous emptying during the period of deflation. This position will be achieved by resting the elbows on foam pads and supporting the hands with pillows. Cuffs will be placed on the widest part of both forearms and a smaller cuff will be placed around each wrist. The non-infused arm is used as a contemporaneous control to account for any minor changes in FBF affecting both arms, *e.g.* emotional stress or temperature changes.

A catheter will be inserted into the brachial artery of the nondominant arm according to standard hospital procedures. A standard arterial cannula will be used. The artery will be palpated at the elbow of the non-dominant arm. The skin will be cleaned with alcohol after which the artery is cannulated transcutaneously. A small infusion of saline will be connected to maintain the line opened.

After cannulation there will be a resting period of approximately 25 min. At the end of this resting period, baseline measurements of FBF will be performed.

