The subject will receive ascending doses of C21 (3, 10, 30, 100 and 200 μ g/min) through local i.a. infusions for 5 min/dose with an infusion rate of 1 mL/min or 2 mL/min for the 200 μ g/min dose. The start -and stop times of the infusions will be recorded. Measurements of FBF will be performed in both arms simultaneously during the last 2 min of each infusion. The C21 doses will be separated by a wash-out period of at least 15 min. At the end of each wash-out period FBF will be measured and a baseline value for the next dose be recorded.

For each FBF measurement, an inflation pressure of 60 mmHg will be used for intervals of approximately 7 sec followed by approximately 8 sec of deflation. This cycle will be repeated approximately 8 times during the last 2 min of each infusion. The wrist cuff will be inflated to supra-systolic pressures within 30 sec before each measurement to exclude the hand circulation. Changes in forearm volume will be measured using strain-gauges placed around the widest part of the forearms. A measure of blood flow to that part of the forearm enclosed by the two cuffs is provided, expressed as mL per 100 mL of forearm volume per minute. Actual forearm volume can be estimated by calculation, assuming the forearm is a simple truncated cone, or by simple water displacement.

When the last C21 dose has been administered, the infusion will be discontinued and there will be a resting period of 20 min. At the end of this resting period, FBF will be measured and a baseline value for the first sodium nitroprusside dose will be recorded.

Infusions of sodium nitroprusside solution (Nipruss[®]) will be performed as a positive control, using the same methodology as described above. Ascending doses of 0.8, 1.6, and 3.2 μ g/min will be administered.

After removal of the arterial catheter a compression bandage will be applied to prevent bleeding.

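### The infusion rate doubles only at the 200 µg/min C21 dose and no volume-matched baseline is specified, so any effect of infused volume cannot be told apart from drug effect there

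*Combined protocol and SAP*

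**What the plan says.** **Infusion rates.** Section 10.5 states that the ascending C21 doses "will be administered to each subject with an infusion rate of 1 mL/min or 2 mL/min for the 200" µg/min dose. Table 10.5-1 lists 1 mL/min for 3, 10, 30 and 100 µg/min and 2 mL/min for 200 µg/min alone. The synopsis agrees: for the top dose, "the infusion rate will be 2 mL/min". All three nitroprusside doses run at 1 mL/min.

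**Sequence.** Section 9.9 rules out randomisation and adds that "all subjects will receive the same IMP and undergo the same study procedures". Rate and dose are therefore paired in the same way in everyone.

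**Baselines.** Section 11.2.1 describes a rest after cannulation, then: "At the end of this resting period, baseline measurements of FBF will be performed". For later doses: "At the end of each wash-out period FBF will be measured and a baseline value for the next dose be recorded". The only fluid named outside the drug infusions is in the same section: "A small infusion of saline will be connected to maintain the line opened". No rate is given, and the section does not say whether the drip runs during flow readings or during drug infusion.

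**Control arm.** Section 11.2.1: "The non-infused arm is used as a contemporaneous control to account for any minor changes in FBF affecting both arms".

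**Analysis.** Section 17.5.1 summarises percent change from the dose-specific baseline. Section 17.5.2 models the natural logarithm of the maximum FBF, with dose as a class variable and subject as random. It names no term for baseline, infusion rate or the control arm.

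**The concern.** Drug readings in the infused arm are taken with 1 or 2 mL/min entering the brachial artery. Baseline readings are taken with whatever the keep-open drip delivers. If infused volume has any effect on measured flow, percent change carries it together with the drug response. The term would differ between the top dose and the other four.

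Nothing in the plan isolates it. There is no vehicle period. The non-infused arm receives no fluid, so it can correct only for changes common to both arms, and Sections 17.5.1 and 17.5.2 do not say how that arm enters the analysis.

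The position matters. Section 8.2.1 says the 200 µg/min dose was chosen so that the full curve is obtained. Whether the response flattens is judged largely from 100 versus 200 µg/min, the only adjacent pair of C21 doses that differs in volume rate.

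**Working it through.** **Inputs**
- Rates, concentrations and 5 min duration: Table 10.5-1.
- Flow: Section 6.4 says "forearm blood flow (FBF) (<50 mL/min) is around 100-fold lower than cardiac output", which is an upper figure only. A range of 20 to 50 mL/min is assumed here. The lower end fits Section 6.6.2, which puts the local concentration at the top dose well below 10 µg/mL: 200 µg/min ÷ 10 µg/mL = 20 mL/min, so flow should lie above that.
- Drip rate: not stated. Taken as 0, then as 0.5 mL/min (assumption).
- Number of subjects: 5 (Section 17.2). The plan gives no SD, so a within-subject SD of 0.1 to 0.3 on the log scale is assumed.

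**1. The plan's own figure.** Rate × concentration × 5 min gives 15, 50, 150, 500 and 1,000 µg. The sum is 1,715 µg = 1.715 mg, as stated in Section 6.6. The infused volumes are 5, 5, 5, 5 and 10 mL.

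**2. Can rate and dose be separated?** The five dose indicators have rank 5. Rate equals 1 × (indicators for 3, 10, 30 and 100) + 2 × (indicator for 200), so adding it leaves the rank at 5. Rate is fully aliased with the 200 µg/min level, and no analysis of the planned data can separate the two.

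**3. Upper bound of the volume term in percent change.** If every infused mL adds to inflow and the drip is 0, the term is rate ÷ flow.

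| Flow (mL/min) | 1 mL/min | 2 mL/min |
|---|---|---|
| 50 (ceiling in the plan) | 1/50 = 2% | 2/50 = 4% |
| 25 (assumed) | 1/25 = 4% | 2/25 = 8% |
| 20 (assumed) | 1/20 = 5% | 2/20 = 10% |

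**4. Allowing for the drip.** If it ran at 0.5 mL/min at baseline and stopped during dosing, the term is (rate − 0.5) ÷ (flow + 0.5).
- Flow 50: 0.5/50.5 = 1.0% and 1.5/50.5 = 3.0%.
- Flow 25: 0.5/25.5 = 2.0% and 1.5/25.5 = 5.9%.

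No single drip rate brings both terms to zero.

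**5. Effect on the dose-response model.** With no drug effect, full addition and no drip, the least-squares means are equal from 3 to 100 µg/min. The mean at 200 µg/min is higher by ln[(flow + 2)/(flow + 1)]:
- Flow 50: ln(52/51) = 0.019, or 2.0%.
- Flow 25: ln(27/26) = 0.038, or 3.8%.

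**6. Scale against random error.** The 95% half-width of a pairwise dose contrast is t(0.975, 16 df) × SD × √(2/5), with 16 = (5 − 1) × (5 − 1) degrees of freedom.
- SD 0.1: 0.13 on the log scale, about 14%.
- SD 0.3: 0.40, about 50%.

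**The case against.** A reader might infer that infused volume is bound to appear as a drug effect. The documents do not support that. Section 11.2.1 says the forearm swells in proportion to arterial inflow, but not that fluid put into the brachial artery raises that inflow one for one. If downstream resistance sets the flow, infused fluid may displace incoming blood and add little. The percentages above are therefore upper bounds. This objection stands.

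It also stands that the plan is silent on the drip rather than explicit about a mismatch. What can be said is that no matched baseline is specified and that one fixed rate could not match two infusion rates.

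The size argument stands in part. At the one flow figure in the plan the bound is 2% and 4%, well inside the random error of five subjects, and the primary analysis is descriptive with no success threshold. But random error is as likely to go down as up, whereas a volume effect would recur in every subject and point towards the expected vasodilatation.

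Finally, a matched baseline alone would leave the Section 17.5.2 model unchanged, because that model has no baseline term. This is correct, and the fix has to cover it.

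**Conclusion.** The concern holds in a limited form. The 2 mL/min rate occurs only at 200 µg/min, in every subject, and no volume-matched baseline is specified. Any volume effect would be counted as drug effect in the percent-change endpoint, and could not be separated from drug effect in contrasts of 200 µg/min with lower doses. Contrasts among 3, 10, 30 and 100 µg/min share one rate and are not affected.

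The possible size is 2% and 4% (1 and 2 mL/min) at a flow of 50 mL/min, and up to 5% and 10% at an assumed 20 mL/min. These figures assume full addition of infused fluid and no drip at baseline, and the truth may be lower. The term is small beside random error, but it would be systematic and in the direction of the expected effect.

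This is a cheap improvement and does not invalidate the trial. It has to be made before dosing: the separate statistical analysis plan announced in Section 17 cannot recover baselines that were never recorded.

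**What to change.** 1. In Section 11.2.1, record each FBF baseline with 0.9% saline running through the same line at the volume rate of the infusion that follows. With no drug effect, the volume term in percent change is then zero at every dose by construction.
2. State the keep-open drip rate and whether the drip runs during flow readings and during drug infusion.
3. In Section 17.5.2, express the outcome relative to the matched baseline, for example as the ln of the ratio of FBF to the dose-specific baseline. Alternatively, report the saline readings at 1 and 2 mL/min beside the 100 versus 200 µg/min contrast. These readings also give a within-subject estimate of the volume effect, which the present design cannot provide.
4. Treat subtraction of infusion rate ÷ forearm volume as a sensitivity analysis at most. It over-corrects if infused fluid displaces inflow, most at the top dose, where it would favour a false plateau. Section 11.2.1 says forearm volume can be estimated, but Table 8.1-1 does not schedule that measurement.

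Drug doses, their order and the drug infusion rates are unchanged.

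**Cost.** A pump setting on a line already in place, and some tens of mL of saline. If run for 5 min before all eight infusions: (4 × 1 + 1 × 2) × 5 = 30 mL for C21, plus 3 × 1 × 5 = 15 mL for nitroprusside, 45 mL in total per session.
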